CMAI	Cohen-Mansfield Agitation Inventory
CMH	Cochran Mantel Haenszel
CPK	Creatine phosphokinase
CYP	Cytochrome P450
DIEPSS	Drug Induced Extra-Pyramidal Symptoms Scale
EQ-5D-5L	EuroQol 5 dimension 5 level health questionnaire
FAS	Full analysis set
FCS	Fully Conditional Specification
HDL	High-density lipoprotein
IDMC	Independent data monitoring committee
IMP	Investigational medicinal product
LDH	Lactate (lactic acid) dehydrogenase
LDL	Low-density lipoprotein
LOCF	Last observation carried forward
MAR	Missing At Random
MedDRA	Medical Dictionary for Regulatory Activities
MMRM	Mixed models for repeated measures
MMSE	Mini-Mental State Examination
MNAR	Missing Not At Random
OC	Observed cases
QTc	QT corrected for heart rate
QTcB	QT corrected for heart rate by Bazett's formula
QTcF	QT corrected for heart rate by Fridericia's formula
QTcN	QT corrected for heart rate by FDA Neuropharmacological Division
~	

formula

Protocol 331-102-00088

S-STS	Sheehan Suicidality Tracking Scale
TEAE	Treatment-emergent adverse event
TITAL	TT 11 1. 0 1

ULN Upper limits of normal

1 Introduction

This statistical analysis plan documents in detail the statistical analysis methods planned for the clinical study report of Trial 331-102-00088.

2 Trial Objectives

The objective of the trial is to evaluate the superiority of brexpiprazole 1 or 2 mg over placebo after a 10-week treatment regimen for agitation associated with dementia of the Alzheimer's type in patients who require medication, to investigate the safety of brexpiprazole, and to identify the optimum dose.

3 Trial Design

3.1 Type/Design of Trial

This is a multicenter, randomized, double-blind, placebo-controlled, parallel-group comparison trial to evaluate the efficacy and safety of brexpiprazole in patients with agitation associated with dementia of the Alzheimer's type who require medication. The overview of the trial design is shown in Figure 3.1-1.

The trial consists of a screening period, a treatment period, and a follow-up period. The investigator or subinvestigator will explain the details of the trial to a prospective subject (if the investigator or subinvestigator judges that the subject is incapable of providing informed consent or if the subject is hospitalized for reasons related to medical protection, the subject's legally acceptable representative must provide written consent, and even when written consent is obtained from the legally acceptable representative, the subject should be given an explanation appropriate to his or her level of understanding and, if possible, should also provide written consent) and their caregivers using the explanatory materials and informed consent form (ICF) and obtain written consent for participation in the trial from the patient (or their legally acceptable representatives) and caregivers. The subject's clinical course will be followed in the same environment (see Section 3.4.2 Inclusion Criteria, 4 of the protocol) such as hospitalization in the same medical facility, institutionalization in the same care facility, and continued care at home from at least 3 weeks before baseline evaluation up to the completion of the examinations scheduled at the completion or discontinuation of investigational medicinal product (IMP) administration. After obtaining consent from the patient (or their legally acceptable representatives) and caregiver, the investigator or subinvestigator will perform the specified observations, tests, and investigations to confirm the subject's eligibility before IMP allocation. Subjects who are judged to be eligible in the screening examination and baseline evaluation will be randomized to the brexpiprazole 1 mg, brexpiprazole 2 mg, or

placebo group. The IMP allocation will be performed using a dynamic allocation method to minimize bias in background factors (medical care category, prior use of antipsychotics, Cohen-Mansfield Agitation Inventory (CMAI) total score in baseline assessment) among the treatment groups. Duration of IMP treatment is 10 weeks. The subject will receive brexpiprazole or placebo for 10 weeks according to Section 3.2 Trial Treatment, and undergo periodic observations, tests, and investigations to assess efficacy and safety. The subject will return to the trial site 28 days after the completion of IMP administration for follow-up observation. Discontinued subjects will also undergo follow-up observation.

For subjects who discontinued the trial during the treatment period, the examination at discontinuation will be performed.

The trial period of each subject is from the date of informed consent to the end date of follow-up observation. If subjects have transitioned to the extension trial and commenced IMP administration, follow-up observation will not be performed. In such a case, the trial period is until the end date of evaluation at Week 10 (Day 71).

[figure not shown]

Figure 3.1-1 Trial Design

Follow-up observation will not be performed for subjects who have transitioned to the extension trial and commenced IMP administration.

3.2 Trial Treatments

The IMP will be administered orally as one tablet once a day for 10 weeks. The doses of brexpiprazole for each group are shown in Table 3.2-1. Although the temporal relationship between IMP administration and meals will not be considered, subjects should take the IMP at the specified time in so far as possible. Dose reduction is not

allowed during the trial, and if there are tolerability issues, administration of the IMP will be discontinued.

Table 3.2-1 Doses of IMPs			
Group	Day 1-7	Day 8-14	Day 15-70
Brexpiprazole 2 mg	0.5 mg	1 mg	2 mg
Brexpiprazole 1 mg	0.5 mg	1 mg	1 mg
Placebo	0 mg	0 mg	0 mg

The dose will be increased to 1 mg after evaluation at Week 1 (Day 8) and to 2 mg after evaluation at Week 2 (Day 15).

3.3 Trial Population

A total of 407 male and female patients (brexpiprazole 2 mg, 148 subjects; brexpiprazole 1 mg, 111 subjects; placebo 148 subjects) with agitation associated with dementia of the Alzheimer's type who require medication will be enrolled in the trial.

3.4 Trial Visit Window

For all endpoints, acceptable windows for analysis are specified, and analysis should be based on the analysis time points regardless of time points recorded on the case report form.

Acceptable windows for analysis are shown in Table 3.4-1. Day 1 is defined as the day when treatment with the IMP begins. If multiple data exist within an acceptable window, the last data within the window will be used in analysis. Data obtained 7 days or later after the final dosing will be excluded from the analysis.

Table 3.4-1 Acceptable Windows for Analysis		
Week	Target Day	Trial Day Interval
Baseline	1	- 1
Week 1	8	2 - 11
Week 2	15	12 - 22
Week 4	29	23 - 36
Week 6	43	37 - 50
Week 8	57	51 - 64
Week 10	71	65 - 78

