^gBlood pressure and pulse rate will be measured in the order of supine, sitting, and standing positions.

^hEligibility will be assessed based on consecutive triplicate ECG measurements (central reading). The third measurement can be omitted if neither the first nor second measurement (central reading) meets the exclusion criteria.

- ¹Pregnancy test (HCG test) will be performed for WOCBP only. If urinary test is positive, serum test will be performed.
- ^JBlood sampling will be performed before IMP administration if the IMP is administered in Week 10 but does not need to be performed at the time of discontinuation.
- ^kIf blood sampling is not performed for any other test item or for some reason cannot be performed at the time of baseline evaluation, or if blood resampling is necessary, blood sampling will be performed during the trial period.

^lOptional

^mIf for some reason it is not possible to perform blood sampling at this time or if blood resampling is necessary, blood sampling will be performed during the trial period.

Table 3.8-2Allowable Time Windows for Evaluations, Tests, and Observations						
Test Point		Base Date	Allowable Time Window From the Base Date			
Screening period		At the start of screening	Day -42 to Day -2			
Baseline evaluation date		Day 1	Day -1 or Day 1			
Week 1		Day 8	Day 6 to Day 10			
Week 2		Day 15	Day 13 to Day 17			
Week 4		Day 29	Day 27 to Day 31			
Week 6		Day 43	Day 40 to Day 46			
Week 8		Day 57	Day 54 to Day 60			
Week 10		Day 71	Day 68 to Day 78			
Follow-up period ^a		28 days after the final administration of IMP	23 to 35 days after the final administration of IMP			

^aFollow-up observation will not be performed for subjects who have transitioned to the extension trial and commenced IMP administration.

The date of starting IMP administration is designated as Day 1.

All baseline observations, tests, and evaluations will be performed on the day before the start of IMP administration (Day -1) and the day of starting IMP administration (Day 1). CMAI, CGI-S,

, and must be performed on the same day.

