3.8.1.5 Examination at Discontinuation

At discontinuation, the investigator or subinvestigator will perform the observations, tests, and assessments shown in Table 3.8-1 as promptly as possible, within the same day if possible, after discontinuation has been decided and will record the results along with the date of visit. If at time of discontinuation, the subject or caregiver refuses any of the tests or if the investigator or subinvestigator judges that tests cannot be performed due to an emergency, only those observations, tests, and assessments that are feasible will be performed.

3.8.1.6 Follow-up Observation (Twenty-eight Days After Completion or Discontinuation of IMP Administration)

The investigator or subinvestigator will perform the observations, tests, and assessments shown in Table 3.8-1 and record the results and date of visit. These observations, tests, and assessments will also be performed in discontinued subjects unless the subject or caregiver refuses any of the tests or the investigator or subinvestigator judges that tests cannot be performed due to an emergency. Follow-up observation will not be performed for subjects who have transitioned to the extension trial and commenced IMP administration.

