6.6.5.2 DIEPSS, AIMS, and BARS

For DIEPSS total score (total of scores for items 1 through 8) and score for each DIEPSS item, AIMS total score (total of scores for items 1 through 7) and score for each of the 3 global judgment items (items 8 through 10), and BARS, descriptive statistics of actual measurements and changes from baseline at each time point will be calculated for each treatment group and for the overall brexpiprazole group.

In addition, using the LOCF data set, analysis will be performed by the ANCOVA model with treatment group, medical care category (hospitalized or outpatient), and prior use of antipsychotics (yes or no) as factors and baseline as a covariate. Least square means of each treatment group and differences in least square means between each brexpiprazole group and the placebo group, as well as the two-sided 95% CIs will be determined.

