6.11 Analysis of Other Endpoints

Analysis of other endpoints will be performed using the safety analysis set. Baseline is defined as the last data obtained prior to initiation of IMP treatment in the trial.

- ADCS-ADL
- MMSE
- EQ-5D-5L

For ADCS-ADL total score, MMSE total score and each item of EQ-5D-5L, descriptive statistics of actual measurements and changes from baseline at each time point will be calculated for each treatment group and for the overall brexpiprazole group.

In addition, using the LOCF data set, analysis will be performed by the ANCOVA model with treatment group, medical care category (hospitalized or outpatient), and prior use of antipsychotics (yes or no) as factors and baseline as a covariate. Least square means of each treatment group and differences in least square means between each brexpiprazole group and the placebo group, as well as the two-sided 95% CIs will be determined.

7 Management of Investigational Medicinal Product

Refer to the investigator's brochure on brexpiprazole and the separately-specified manual for details regarding IMP management.

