CT-10.5.1	Incidence of Laboratory Test Values With Potential Clinical Relevance - Prolactin
	(Safety Analysis Set)
CT-10.5.2	Listing of Laboratory Test Values With Potential Clinical Relevance - Prolactin
CT 10.61	(Safety Analysis Set)
CT-10.6.1	Incidence of Treatment-emergent Significant Change in Lipids (Safety Analysis Set)
CT-10.6.2	Listing of Treatment-emergent Significant Change in Lipids (Safety Analysis Set)
CT-10.7.1	Incidence of Treatment-emergent Significant Change in Glucose (Safety Analysis
01 101/11	Set)
CT-10.7.2	Listing of Treatment-emergent Significant Change in Glucose (Safety Analysis Set)
CT-11.1	Mean Change From Baseline in Vital Signs (Safety Analysis Set)
CT-11.2	Incidence of Potentially Clinically Relevant Abnormalities in Vital Signs (Safety
OT 11.2	Analysis Set)
CT-11.3	Listing of Potentially Clinically Relevant Abnormalities in Vital Signs (Safety
CT-11.4	Analysis Set) Summary of Mean Change From Baseline to Double Blind Treatment Period by
	Study Week in Body Weight (kg) (Safety Analysis Set)

CT-11.5	Summary of Mean Change From Baseline to Double Blind Treatment Period by
CT-11.6	Study Week in BMI (kg/m^2) (Safety Analysis Set) Incidence of Potentially Clinically Relevant Weight Gain or Loss by Baseline BMI
	(Safety Analysis Set)
CT-12.1	Mean Change From Baseline in ECG Results (Safety Analysis Set)
CT-12.2	Shift Tables of ECG (Safety Analysis Set)
CT-12.3	Incidence of Categorical Increases in QT Evaluations (Safety Analysis Set)
CT-12.4	Incidence of Potentially Clinically Relevant Abnormalities in ECG
	Evaluations (Safety Analysis Set)
CT-12.5	Listing of Potentially Clinically Relevant Abnormalities in ECG Evaluations (Safety
	Analysis Set)
CT-13.1	Summary of Mean Change From Baseline to Double Blind Treatment Period by
CIT. 12.2	Study Week in DIEPSS (Safety Analysis Set)
CT-13.2	Summary of Mean Change From Baseline to Double Blind Treatment Period by
CT-13.3	Study Week in AIMS Total Score and Item Scores 8, 9 and 10 (Safety Analysis Set) Summary of Mean Change From Baseline to Double Blind Treatment Period by
C1-13.3	Study Week in BARS, Global Clinical Assessment of Akathisia (Safety Analysis
	Set)
CT-14.1	Summary of Mean Change From Baseline to Double Blind Treatment Period by
	Study Week in Sheehan-STS Score (Safety Analysis Set)
CT-14.2	Summary of Mean Change From Baseline to Double Blind Treatment Period by
	Study Week in Sheehan-STS - Total Score (Safety Analysis Set)

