LAB-2	Laboratory Test Results: Hematology (Randomized Subjects)
LAB-3	Laboratory Test Results: Urinalysis (Randomized Subjects)
LAB-4	Laboratory Test Results: Other Laboratory Tests (Randomized Subjects)
LAB-5	Pregnancy Test (Randomized Subjects)
EFF-1	Cohen-Mansfield Agitation Inventory (CMAI) (Randomized Subjects)
EFF-2	Clinical Global Impression - Severity of Illness (CGI-S) (Randomized Subjects)
EFF-3	Clinical Global Impression - Improvement (CGI-I) (Randomized Subjects)
EFF-4	
EFF-5	
PDATA-1.1	Inclusion and Exclusion Criteria (Randomized Subjects)
PDATA-1.2	Inclusion and Exclusion Criteria (Screening Failure)
PDATA-2	Subject Randomization List (Randomized Subjects)
PDATA-3	Study Completion Status and Reasons for Discontinuation (Randomized Subjects)
PDATA-4	Medical History (Randomized Subjects)
PDATA-5	Alzheimer's Disease History (Randomized Subjects)
PDATA-6	Patient Care (Randomized Subjects)
PDATA-7.1	Prior and Concomitant Medications (Antipsychotic) (Randomized Subjects)
PDATA-7.2	Prior and Concomitant Medications (Antidementia Drug) (Randomized Subjects)
PDATA-7.3	Prior and Concomitant Medications (Other) (Randomized Subjects)
PDATA-7.4	Prior and Concomitant Therapy (Randomized Subjects)
PDATA-8	Physical Examination (Randomized Subjects)
PDATA-9	Vital Signs (Randomized Subjects)
PDATA-10	Electrocardiogram Results (Randomized Subjects)
PDATA-11.1	Sheehan-Suicidality Tracking Scale (S-STS) - Other than Q15 and Q16 (Randomized Subjects)
PDATA-11.2	Sheehan-Suicidality Tracking Scale (S-STS) - Q15 (Randomized Subjects)
PDATA-11.3	Sheehan-Suicidality Tracking Scale (S-STS) - Q16 (Randomized Subjects)
PDATA-12	Drug-Induced Extrapyramidal Symptoms Scale (DIEPSS) (Randomized Subjects)
PDATA-13	Barnes Akathisia Rating Scale (BARS) (Randomized Subjects)
PDATA-14	Abnormal Involuntary Movement Scale (AIMS) (Randomized Subjects)
PDATA-15	Mini-Mental State Examination (MMSE) (Randomized Subjects)
PDATA-16	Alzheimer's Disease Cooperative Study - Activities of Daily Living (ADCS-ADL) (Randomized Subjects)
PDATA-17	EuroQol 5 Dimension 5 Level Health Questionnaire (EQ-5D-5L) - Proxy Version (Randomized Subjects)
PDATA-18	EuroQol 5 Dimension 5 Level Health Questionnaire (EQ-5D-5L) (Randomized Subjects)
PDATA-19	Pharmacokinetic Blood Draw Time (Randomized Subjects)
PDATA-20	CYP2D6 Genetic Test (Randomized Subjects)
PDATA-21	Blood Draw Time for DNA Storage and Biomar ker (Randomized Subjects)
PDATA-22	Post-treatment Follow-up (Randomized Subjects)

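### SAP 3.4 keeps the follow-up ratings of five scales out of the by-arm summaries without listing this in SAP 15; secondarily, its 7-day cut-off conflicts with the Day 78 limit of the Week 10 window

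*SAP*

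**What the plan says.** **Collection.** Protocol Table 3.8-1 marks DIEPSS, AIMS, BARS, ADCS-ADL and MMSE in the follow-up column; CMAI, S-STS and EQ-5D-5L are not marked. Table 3.8-2 places the visit "23 to 35 days after the final administration of IMP". Protocol 3.8.1.6 adds that "These observations, tests, and assessments will also be performed in discontinued subjects", apart from refusals and emergencies. Subjects who have started IMP in the extension trial have no follow-up visit. Protocol 3.8.5.1 allows a telephone interview for ADCS-ADL at this visit only.

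**Protocol analysis.** For DIEPSS, AIMS and BARS, protocol 6.6.5.2 says that "descriptive statistics of actual measurements and changes from baseline at each time point will be calculated for each treatment group". Protocol 6.11 plans the same, by time point and by group: "For ADCS-ADL total score, MMSE total score and each item of EQ-5D-5L, descriptive statistics of actual measurements and changes from baseline". Neither section mentions follow-up.

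**SAP analysis.** SAP 3.4 covers all endpoints and says that "analysis should be based on the analysis time points regardless of time points recorded on the case report form". The rows of Table 3.4-1 are baseline and Weeks 1, 2, 4, 6, 8 and 10, the last window being Days 65 to 78. Then comes the cut-off: "Data obtained 7 days or later after the final dosing will be excluded from the analysis". The Appendix 5 tables for the five scales (CT-13.1 to CT-13.3, CT-15.1, CT-15.2) have titles that open "Summary of Mean Change From Baseline to Double Blind Treatment Period by" study week. Appendix 6 holds subject listings, such as the one whose title opens "Drug-Induced Extrapyramidal Symptoms Scale (DIEPSS) (Randomized Subjects". SAP 15 declares that LOCF was replaced in the ANCOVA of safety and other endpoints. It mentions neither follow-up nor the cut-off.

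**Week 10.** The visit window is Days 68 to 78 in protocol Table 3.8-2 and the analysis window is Days 65 to 78 in SAP Table 3.4-1. The dosing tables in both documents end on Day 70.

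**The concern.** The protocol sends subjects back for movement-disorder, daily-living and cognition ratings after treatment has stopped, discontinued subjects included. A reader of the protocol could expect those ratings to be compared descriptively between arms. Under the SAP they are not, and the SAP section meant for departures from the planned analyses does not record this. At stake is a small part of the safety reporting: how the scale scores stand in each arm about four weeks after the last dose.

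The same cut-off also bears on the primary endpoint. A Week 10 CMAI rating that both documents accept as in window can drop out of the primary MMRM only because it came 7 or 8 days after the last dose.

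**Working it through.** The plan gives no figure for the follow-up point. Its power figures bear only on the Week 10 point and are reproduced in step 5.

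**1. Day count.** Protocol 3.8.1.4 equates seven days after administration with Day 8, so n days after Day D is Day D + n.

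**2. Cut-off against follow-up.** For a last dose on Day D, follow-up falls on Days D + 23 to D + 35. The shortest gap is 23 days and the cut-off acts from 7 days. Since 23 ≥ 7 for every D, the cut-off alone removes every follow-up rating, including from last-assessment and worst-value summaries.

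**3. What the missing row does by itself.** The post-baseline windows of Table 3.4-1 run without gaps from Day 2 to Day 78.

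| Last dose D | Follow-up days | Position |
|---|---|---|
| 56 or later | D + 23 ≥ 79 | all after Day 78 (D = 70 gives Days 93-105) |
| 44 to 55 | mixed | partly inside the Week 10 window |
| 43 or earlier | D + 35 ≤ 78 | all inside a treatment-visit window (D = 1 gives Days 24-36, Week 4; D = 28 gives Days 51-63, Week 8) |

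The missing row alone therefore excludes all follow-up days only for D ≥ 56. Adding a row without an exemption from the cut-off would change nothing. Deleting the cut-off would let follow-up ratings of early discontinuers into the Week 4 to Week 10 windows.

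**4. Share of the schedule.** DIEPSS is scheduled after baseline at Weeks 1, 2, 4, 6, 8 and 10 and at follow-up, so follow-up is 1 of 7. AIMS, BARS, ADCS-ADL and MMSE are scheduled at Week 10 and follow-up, so it is 1 of 2. These are schedule cells, not numbers of observations.

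**5. Week 10.** A visit on Day V is dropped when V − D ≥ 7. Among the 11 protocol days (68 to 78):

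- D = 70: Days 77 and 78 are lost (2 of 11).
- D = 71: Day 78 is lost (1 of 11).
- D ≥ 72: none is lost.

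For D ≥ 70 the affected last-dose/visit pairs are 70/77, 70/78 and 71/78. The CMAI look-back is the 14 days before the visit (protocol 3.8.2.1), Days V − 14 to V − 1. Off-drug days in it are 6 for 70/77, 7 for 70/78 and 6 for 71/78, against 5 for 70/76, which the SAP accepts.

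The planned power reproduces with a two-sided 5% noncentral t calculation, noncentrality 5.35 / [15.06 × √(1/n₁ + 1/n₂)]: 86.1% for 148 against 148 and 80.5% for 148 against 111. If an assumed share of Week 10 ratings were lost equally in all arms, a complete-case t test, which is pessimistic for an MMRM, would give 85.8% and 80.1% at 1%, 85.4% and 79.7% at 2%, and 84.3% and 78.4% at 5%. The documents give no such share.

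**The case against.** SAP 3.4 states the exclusion openly, for all endpoints, and the table titles repeat the limit. Protocol section 6 leaves detail to the SAP and sets no analysis windows of its own. The protocol wording on time points does not name follow-up, and protocol 3.11 ties evaluation of the trial objectives to the treatment period. A by-arm follow-up table would also describe a group selected after randomisation, because extension entrants are missing from it. Most of this stands. A reader might infer that the SAP hides the omission or breaks an explicit protocol commitment; the documents support neither. What remains is that the protocol schedules these ratings and does not exclude them from its planned summaries, while the SAP does, and SAP 15 is silent.

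A reader might also infer that post-treatment movement problems vanish from the comparison. They do not if reported as adverse events: SAP 9.2 tabulates onset with a category for the time after trial treatment, and SAP 9.2.1 summarises extrapyramidal events by arm. Nor can it be said that the follow-up ratings are discarded. They presumably appear in the listings, although this is inferred from the listing titles.

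On Week 10, dosing past Day 70 is foreseen. IMP is supplied up to the next assessment (protocol 3.8.1.4), a dose at Week 10 is contemplated (protocol 3.8.4.1), and SAP 9.1 has an exposure category above 70 days. Keeping ratings well off drug out of an on-treatment analysis is also a fair purpose. A reader might take the conflict as a threat to the primary analysis; the documents do not show one.

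**Conclusion.** The point holds as a minor one. The follow-up ratings of five scales are collected, are left out of the by-arm summaries by the 7-day cut-off for every possible last-dose day, and are not listed as a change in SAP 15. The gap is limited to scale scores. The conclusion rests on reading the protocol's unqualified time points as not excluding follow-up, and on the Appendix 5 titles meaning what they say. How many subjects have follow-up ratings is not known, because the number entering the extension trial is not given.

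The Week 10 conflict is real but secondary. It arises only if dosing stops on Day 70 or 71 (or earlier, when more days are lost) and the visit is late in the window. The number affected is unknown and may be zero.

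**What to change.** **Follow-up.** In SAP 3.4, add a separate follow-up time point, 23 to 35 days after the last dose, for the five scales. State that it is exempt from the 7-day cut-off and summarised descriptively by arm only. Keep it out of the treatment-visit windows and out of the last-assessment, worst-value and ANCOVA derivations. Footnote that extension-trial entrants have no such visit, so the summary covers a selected subset. Keep the cut-off for the treatment-visit windows. If the sponsor prefers the omission, list it in SAP 15.

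**Week 10.** Reconcile the cut-off with the Day 78 limit in SAP 3.4 before unblinding. One way is to retain in-window Week 10 ratings of subjects who completed the planned treatment period. The definition needs care so that near-identical cases are treated alike: a bare rule of last dose on Day 70 or later would keep 70/78 (8 days after the last dose) but drop 69/76 (7 days). It should not cover all completers under protocol 3.11, which disregards whether every dose was taken. A subject who stopped on Day 50 and was rated on Day 71 has all 14 look-back days off drug and should stay excluded. Report how many values are affected and, if any are, repeat the primary MMRM with the cut-off applied to all subjects.

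**Cost.** SAP wording, one descriptive time point in the tables of five scales, and at most one repeat of the primary model, all on data already collected. The downside of the Week 10 change is up to 7 off-drug days in the CMAI look-back, against 5 for a Day 76 visit that is accepted now.
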